Official title: Lidocaine Infusion as a Treatment for Cocaine Relapse and Craving

NCT number: NCT01929343

Document date: May 21, 2015

The University of Texas Southwestern Medical Center at Dallas Institutional Review Board

Protocol Template (for Investigator Initiated Studies)

1. Title

Lidocaine Infusion as a Treatment for Cocaine Relapse and Craving

2. Principal Investigator and Co-Investigator

PI: [name]. Co-Investigators: [name] M.D., Ph.D.; [name].; [name].; [name].

3. Sponsor of the Study

NIH-NIDA

4. Investigational New Drug (IND)/Investigational Device Exemption (IDE)

IND 119175 for Lidocaine Hydrochloride Injection

5. Purpose of the Study, Including the Hypothesis to be Tested

Pharmacologic approaches have been generally unsuccessful in decreasing cocaine use in addicted patients and behavioral approaches have limited utility. While some medications and novel approaches show promise, there are presently no FDA approved drugs for the treatment of cocaine addiction. Furthermore, pharmacologic approaches directly targeting monoamine, GABAergic, and NMDA receptors have not been fruitful. Thus, the need for novel targets and approaches for cocaine addiction is imperative.

Primary Aim 1: Assess the effects of lidocaine in reducing cue-induced cocaine craving.

Hypothesis P1: Cue-induced craving assessed one week after infusion will be less in patients administered lidocaine+cue-induced relative to those given saline+cue-induced craving or lidocaine alone.

Hypothesis P1b: Physiologic responses to cue-induced craving assessed one week after infusion will be significantly less in patients administered lidocaine relative to those administered saline.

Primary Aim 2: Assess the effects of lidocaine on cocaine use [as measured by urine drug screen (UDS)] and craving for four weeks following lidocaine or saline administration.

Hypothesis P2a: Cocaine use will be significantly less in the patients administered lidocaine [+cue-induced craving] compared to those administered saline+cue-induced craving or lidocaine alone.

Hypothesis P2b: Craving will be significantly less in the patients administered lidocaine+cueinduced craving compared to those administered saline+cue-induced craving or lidocaine alone.

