10/8/2014 Page 1 of 7 A novel treatment approach is to disrupt the neural processes involved in cue-related memories (memory links between the external stimuli associated with drug use and the subjective drug effect). These engrained memories, when reactivated by cues, elicit craving and a return to drug use. Each cue re-exposure, however, requires the re-remembering (or reconsolidation) of the drug cue. Key molecular processes required for memory reconsolidation are NMDA receptor activation, the induction of nitric oxide (NO) synthesis and increased extracellular signal-regulated kinase (ERK) activity. In rodent models, blocking these processes changes the cue-related memory; the cue loses its potency to induce a return to drug self-administration. Lidocaine is an FDA approved medication that inhibits activation of NMDA receptors and suppresses production of NO and ERK. Lidocaine, like cocaine, is a local anesthetic with potent effects as a sodium-channel blocker. Unlike cocaine, lidocaine is essentially devoid of activity at monoamine re-uptake transporters and has no rewarding or addictive properties. As lidocaine suppresses the molecular processes required for drug cue reconsolidation and has relatively specific effects upon the striatal regions necessary for drug cue reconsolidation, lidocaine may offer a novel approach for interfering with memory reconsolidation. Two other Na⁺ channel blockers have also decrease craving and/or substance use in substance-dependent subjects. We propose that the systemic administration of lidocaine following the induction of cue-induced craving, relative to saline plus cue-induced craving or lidocaine without cue-induced craving, will block the reconsolidation of cue memories. This will lead to a reduction in cue-induced craving upon repeated testing as well as subsequent cocaine use and basal craving. If our hypotheses are proven correct, these findings will 1) support a role for lidocaine in cocaine addiction treatment, 2) demonstrate the feasibility and efficacy of attenuating cue-induced memories, and 3) guide the development of a larger study with lidocaine.

7. Concise Summary of Project:

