In this proof-of-concept approach for the treatment of cocaine addition (modeled on a paradigm developed by our group to assess pharmacologic disruptors of PTSD-related trauma memories), the effect of lidocaine infusion following cue-induced craving will be assessed in treatment-seeking, cocaine-addicted outpatients. Immediately following the induction of cue-induced craving, lidocaine or saline will be administered in a double-blind, randomized design. A third arm will also assess lidocaine in the absence of cue-induced craving. One week following the infusion, cue-induced craving will be assessed. Cocaine use and craving (non cue-induced) will be monitored for four weeks.

8. Study Procedures:

66 participants with active cocaine use disorder will be studied. After consent and screening, on Study Day 1, participants will describe scenarios in which they experience cocaine cravings. Participants will also be asked to describe scenarios that they find relaxing. This study session lasts approximately one hour. On Study Day 2, participants will be checked in overnight at Zale Hospital. If the participant is not currently on a residential treatment unit, they may be asked to stay overnight for 3 days prior to Study Day 2. Upon arrival the participants will have a physical exam and drug and pregnancy tests. The following day, scripts will be read to participants and lidocaine (n=22) or saline (n=22) will be administered immediately following craving reactivation. Since lidocaine may be effective in the absence of craving induction, a third group of subjects (n=22) will be given lidocaine but not a craving script. One week later (Study Day 3), craving intensity and physiologic activation following cue-induced craving will be assessed. Costs incurred from these visits will be covered by the research team's funding for this study. Follow-up sessions post-infusion will include 3 times weekly UDS for 4 weeks. Weekly therapy visits conducted for all outpatient participants will be audio recorded for research purposes only. Recordings will not be used for commercial purposes.

If participant is attending a residential treatment program, Study Day 2 will take place one week prior to discharge from their program. Study Day 3 will take place immediately following discharge from their treatment program.

Due to sex differences in craving (106), randomization will be stratified by sex.

9. Sub-Study Procedures:

NA 10/8/2014 Page 2 of 7

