Patients with active DSM-IV other Substance Dependence (except nicotine) within the previous three months, Affective Disorder, Schizophrenic Disorders, or significant cognitive impairment (WTAR<70). Due to the complicating presentation of substance-induced mood or psychotic disorders, these disorders will only be cause for exclusion if symptoms persist upon cocaine abstinence. Patients concomitantly using tricyclic anti-depressants, benzodiazepines, cimetidine, mood stabilizers, opioids, lithium, sympathomimetics, anticonvulsants that act on sodium and L-type channels similar to lidocaine, sedative/hypnotics, β -blockers, or dopamine agonists will be excluded from the study. Participants on stable doses of SSRIs and SNRIs for at least two weeks will not be excluded. Medical conditions that might limit cooperation (e.g. dementia) or put the patient at medical risk (i.e. significant hematologic, hepatic, renal, or cardiovascular pathology - particularly arrhythmias) will be excluded. Patients with congenital or idiopathic methemoglobinemia or patients taking medications associated with increased risk of methemoglobinemia (including sulfonamides, acetaminophen, acetanilid, aniline dyes, benzocaine, chloroquine, dapsone, naphthalene, nitrates and nitrites, nitrofurantoin, nitroglycerin, nitroprusside, pamaguine, paraaminosalicylic acid, phenacetin, phenobarbital, phenytoin, primaguine, guinine) will be excluded. Patients with past or present neurologic disorders (i.e. severe head trauma, transient ischemic attacks, stroke, tumor, etc.) will be excluded. Active suicidal ideation, pregnant or nursing women, and prisoners will be excluded from the study.

12. Sources of Research Material:

Initial screening will consist of questionnaires, routine blood chemistry and cell blood count, EKG, pregnancy test and urine tests for illicit drug use. Questionnaires will include lifetime use of substances (drugs and alcohol), personal psychiatric history, psychiatric history of family members, demographic and medical information, and development of craving script. Subjective measures of craving, mood, and anxiety and physiological measures will be obtained during infusion and reactivation sessions. Measures of craving, mood and urine tests for illicit drug use will be obtained upon follow-up. All measures will be used for research purposes only.

13. Recruitment Methods and Consenting Process:

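### No pre-treatment craving rating under provocation is documented for all three arms, so the Day 3 comparison in P1 loses precision and no change from baseline can be compared with lidocaine alone

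*Combined protocol and SAP*

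**What the plan says.** Section 5 words P1 as a comparison of levels at one time: "Cue-induced craving assessed one week after infusion will be less in patients administered lidocaine+cue-induced relative to those given saline+cue-induced craving or lidocaine alone". It names no baseline and no change score. Section 6 adds a prediction for lidocaine given after cue induction, relative to both other arms: "This will lead to a reduction in cue-induced craving upon repeated testing as well as subsequent cocaine use and basal craving".

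Section 8 sets the design. In total, "66 participants with active cocaine use disorder will be studied". At the infusion session, "lidocaine (n=22) or saline (n=22) will be administered immediately following craving reactivation", while "a third group of subjects (n=22) will be given lidocaine but not a craving script". Then, "One week later (Study Day 3), craving intensity and physiologic activation following cue-induced craving will be assessed"; no arm is excepted. The missing script is deliberate. Section 7 states the purpose: "A third arm will also assess lidocaine in the absence of cue-induced craving".

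On measurement, Section 12 says: "Subjective measures of craving, mood, and anxiety and physiological measures will be obtained during infusion and reactivation sessions". It also lists craving at follow-up. Section 8 has all participants talk through their craving scenarios on Day 1, and Section 15 expects script development to raise craving. Neither section mentions a rating at that session. The baseline battery in Section 13 (cocaine use over the previous 90 days, consequences of drug use, quality of life) contains no craving rating. Section 18 leaves out the biostatistics, as the template allows for NIH-funded work.

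**The concern.** Cue-induced craving differs between people, and no entry criterion requires or measures cue reactivity. With 22 per arm, a pre-treatment reading of something close to the outcome is an obvious way to reduce residual variance and to see whether the arms started alike. For the contrast with lidocaine alone, no such reading is documented. That contrast carries the reconsolidation claim, because it separates an effect on a reactivated memory from a general drug effect on craving. The provocation that could supply a common reading already takes place on Day 1; only the rating is undocumented.

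**Working it through.** **Plan's own figure.** Three arms of 22 give 3 × 22 = 66, which agrees with Section 8. The document gives no alpha, power, effect size or standard deviation (SD), so no sample-size derivation can be reproduced.

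**Scripted cue tests by arm (Section 8).**

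| Arm | n | Infusion session | Day 3 | Tests |
|---|---|---|---|---|
| Lidocaine + cue | 22 | yes, before infusion | yes | 2 |
| Saline + cue | 22 | yes, before infusion | yes | 2 |
| Lidocaine alone | 22 | no | yes | 1 |

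A pre-infusion cue-induced reading is possible in 44 of 66 participants. It also requires the rating to be taken after the script and before the infusion starts, and the document does not state that timing. In the other 22, no change in cue-induced craving can be formed.

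**Precision.** Assumptions, none from the documents: equal variances, outcome in SD units, no dropout, and correlation r between the Day 1 and Day 3 ratings. Covariate adjustment leaves a residual variance of 1 − r², so the equivalent sample per arm is 22/(1 − r²). The small cost of estimating the slope is ignored.

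- r = 0.3: removes 0.09, or 9%; 22/0.91 = 24.2
- r = 0.5: removes 0.25, or 25%; 22/0.75 = 29.3
- r = 0.7: removes 0.49, or 49%; 22/0.51 = 43.1

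As a detectable difference (two-sided 0.05, 80% power, normal approximation), the unadjusted figure is (1.960 + 0.842) × √(2/22) = 2.802 × 0.302 = 0.84 SD. Multiplying by √(1 − r²) gives 0.81, 0.73 and 0.60 SD.

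**Validity without a baseline.** In a simulation of 20,000 trials with 22 per arm, no drug effect and no repeat-exposure effect, the Day 3 t-test rejected in 5.2% against a nominal 5%.

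**What the covariate cannot correct.** At Day 3, lidocaine + cue hears the script a second time and lidocaine alone a first time. If one earlier hearing alone lowered craving by an assumed 0.2, 0.3 or 0.5 SD, this contrast would reject in 10%, 17% or 37% of simulated trials with no drug effect. Lidocaine + cue against saline + cue is not affected in this way, because both have heard it once before.

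**The case against.** The strongest reply is that P1 needs no baseline. It compares randomised arms at Day 3, and randomisation makes that comparison unbiased. This stands. A reader might infer that P1 is invalid or biased by baseline imbalance; the documents do not support that. With a standard error of √(2/22) = 0.302 SD, the chance that two arms differ by more than 0.3 SD on any baseline variable is about 32%. But that is simply the chance of exceeding roughly one standard error, and the standard error of the Day 3 difference already contains that variation.

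A reader might also infer that the trial predicts a reduction within lidocaine alone that it cannot measure. Section 6 predicts no such thing. Its prediction concerns lidocaine after cue induction, and giving no script is the point of the third arm.

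Nor can one say that a common reading is absent from the trial altogether. Section 12 is a short summary, Section 18 omits the biostatistics, and Section 15 refers to a Section IV.E.4 that is not in this document. The supportable statement is that none is documented here. Proxies also exist in all arms: sex is a stratification factor, 90-day use is recorded, and a resting craving rating before infusion may be taken.

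Finally, talking through a scenario is a different provocation from hearing a script, so the correlation may be low. At 0.3 the gain is about two participants per arm. This also stands, and is why a range is shown.

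**Conclusion.** The point holds as an inexpensive gain in precision; it is not a flaw that undermines P1. No pre-treatment craving rating under provocation is documented for all three arms. As a result, the P1 contrasts forgo precision, chance imbalance in cue reactivity cannot be directly checked or adjusted for across the three arms, and change from baseline cannot be compared with lidocaine alone. The gain from a Day 1 rating runs from about 24 to 43 participants' worth per arm instead of 22, for assumed correlations of 0.3 to 0.7. Nothing in the documents says where in that range, or whether inside it, the true value lies. The difference between a first and a second script hearing at Day 3 is a separate limit on interpreting the contrast with lidocaine alone, and it remains after adjustment.

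**What to change.** 1. On Day 1, take the same subjective craving rating from every participant directly after they talk through their craving scenarios. If such a rating is already taken, write it into the protocol.
2. Prespecify that rating, together with sex, as covariates in the P1 Day 3 comparison of all three arms.
3. Make any change analysis from the infusion session to Day 3 secondary and limit it to the two cue arms. Do it only if the infusion-session rating is taken after the script and before the infusion starts, and state that timing.
4. In the report, acknowledge that at Day 3 the cue arms hear the script a second time and lidocaine alone a first time, and that the Day 1 covariate does not correct for this.

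The cost is one brief self-rating in a session of about an hour, plus one model covariate. Participants already past Day 1 will lack the rating, so the analysis plan should say in advance how they are handled.

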Since lidocaine can increase cocaine lethality (122), participants with a positive UDS for cocaine (or amphetamine) or who report stimulant use within the previous 72 hours will not receive an infusion. Women with a positive pregnancy test or who report unprotected heterosexual sex since their previous menses not receive an infusion and will be referred for appropriate care. If an infusion is not administered due to cocaine use, the subject may be rescheduled for another session (at the PIs discretion). If the rescheduled infusion cannot be performed (due to stimulant use or pregnancy), the subject will be terminated from the study and referred for care. In addition, subjects will be observed for at least two hours (approximately one half-life of lidocaine) following the cessation of lidocaine (or saline) infusion. Participants will be discharged to the care of a family member or friend. All participants will receive a 24-hour call-in number to contact research staff in the advent of problems. An IND for the use of lidocaine (administered over one hour in outpatient cocaine-addicted patients during a neuroimaging paradigm) has recently been approved by the FDA using a similar paradigm, including the two-hour wait prior to discharge (IND 115555).

Investigators, other research staff, therapists, and other clinical care staff will be blind to the status of the subjects in the study. If necessary, the blind can be broken by the VHANTX research pharmacist. Breaking the blind would be unlikely, however, as any adverse event experienced during the infusion will be treated acutely with the assumption that the participant is receiving active drug.

As lidocaine is not FDA approved for the treatment of cocaine addiction or to attenuate memory reconsolidation, an IND will be obtained from the FDA for its use in this proposal. In addition, the DSMB will obtain interim unblinded primary outcome measures following the assessment of 15 participants (n=5/group) and 30 participants (n=10/group) (see Section IV.E.4).

At the final follow-up session, all outpatient participants will receive a referral list of local substance use intervention centers, both public sector and private. If a participant's substance use worsens during the study and more intensive treatment is required, the participant will be referred for more intensive treatment and terminated from the study.

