None of the proposed members is a co-investigator or consultant on the proposed grant. Thus, the board will provide an independent review and oversight of the study. The board will meet immediately prior to the initiation of enrollment in the study and again after 10 and 30 participants have been enrolled and at the end of the study. The study's research assistant will present safety data to the board for review, including changes in cocaine use/craving and dropouts prior to cue-memory reactivation and during follow-up. The PI ([name]) will also attend the meeting. In addition, materials provided to the IRB, including serious adverse events leading to death, hospitalization, or ER visits will be forwarded to board members. The board will review preliminary data on adverse events and outcomes. As lidocaine has not previously been assessed for use in the treatment of cocaine addiction or to attenuate memory reconsolidation, the study statistician ([name]) will conduct a blinded analyses of the primary outcome measures after 15 and 30 subjects have been assessed. If notable differences are observed between treatment groups, the research pharmacist will unblind the groups for the DSMB (see Letter from DSMB Chair, [name]). If a pattern begins to emerge and the Board feels that protocol modifications are needed, based on a preponderance of adverse events occurring in a particular treatment group or lidocaine is increasing cocaine craving and/or cocaine use (the opposite of what is hypothesized), it will have the authority to recommend modifications of safety procedures and recommend temporarily or permanently discontinuation of enrollment. However, the final decision on these matters will rest with the local IRBs and NIDA.

16. Procedures to Maintain Confidentiality:

Subject confidentiality will be maintained at all times. Results of the urine drug screens and all other research tests will be strictly confidential. The investigative team will retain all of the information obtained in this research. None of the data will be presented in any publications in such a way to identify a particular subject. All data and copies of executed consent forms will be maintained in the offices of the study personnel at the UT Southwestern Medical Center or VA Medical Center. A Certificate of Confidentiality will be obtained for the study.

17. Potential Benefits:

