Direct Benefit to Participants: The assessment, including a history and physical, routine labs, and diagnostic interview may be some direct benefit to participants. All subjects will receive CBT, which is a beneficial treatment for cocaine dependence. Frequent follow-up visits with study staff have also been shown to have a positive effect on treatment outcome. If lidocaine is effective in disrupting cocaine-cue memories, the group given lidocaine will directly benefit from this intervention. *Direct Benefit to Others:* This study may provide the basis for both a new pharmacological treatment (lidocaine) and new approach (disruption of memory reconsolidation) cocaine dependence.

18. Biostatistics: (omit this section for peer-reviewed research such as cooperative group, or NIH-sponsored studies, and for industry-sponsored research which has been submitted to FDA) Study is funded by NIDA.

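### The exit rule for worsening substance use also ends outcome follow-up, so Primary Aim 2 loses UDS and craving data for a reason tied to the outcome

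*Combined protocol and SAP*

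**What the plan says.** Section 5 sets Primary Aim 2 as the effect of lidocaine on cocaine use, measured by UDS, "and craving for four weeks following lidocaine or saline administration". Hypothesis P2a concerns use and P2b concerns craving. Section 7 repeats the window: "Cocaine use and craving (non cue-induced) will be monitored for four weeks". Section 8 gives the schedule: "Follow-up sessions post-infusion will include 3 times weekly UDS for 4 weeks".

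Section 15 contains the exit rule. It has a joint trigger, "substance use worsens during the study and more intensive treatment is required", and a double consequence: "the participant will be referred for more intensive treatment and terminated from the study".

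The only other text on losses after infusion is in the Data and Safety Monitoring Board part of Section 15, where the board is shown "changes in cocaine use/craving and dropouts prior to cue-memory reactivation and during follow-up". Section 18 (Biostatistics) is left out because the template lets investigators "omit this section for peer-reviewed research such as cooperative group, or NIH-sponsored studies".

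**The concern.** The rule joins two separate things: sending the participant for other care, and ending participation in the study. The first is a clinical decision and is not questioned here. The second removes the participant from the assessments that define Primary Aim 2, and the trigger is closely related to the outcome being measured. Samples already taken remain, but the later ones are never collected, mostly from people who are using.

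If lidocaine works as P2a predicts, more control participants leave and the observed difference tends to shrink. If lidocaine increases use, the loss falls more on the lidocaine arms. That is the harm the monitoring board is asked to watch for, so its view is weakened, although not removed, because it does see dropouts.

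A missing-data rule may exist in a document not supplied. It could score or model the untaken screens, but it could not recover them. Scoring a missed screen as positive also has no counterpart for a craving score (P2b).

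**Working it through.** **What the text fixes.** Section 8 gives 3 UDS per week × 4 weeks = 12 per participant. With 22 per arm and three arms, that is 22 × 12 = 264 per arm and 66 × 12 = 792 in all. An exit at the end of week 1, 2 or 3 loses 9, 6 or 3 of the 12 screens (75%, 50% or 25%). The document gives no termination rate, effect size, alpha or analysis method, so there is no figure of the plan's own to reproduce. Everything below is an assumption chosen to show the range.

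**Hand calculation.** Of n = 22 per arm, let k exit at the end of week w. Those who stay have 40% positive screens; those who exit have 60% before exit and 90% after.

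- Full follow-up: [(n − k)·12·0.40 + k·(3w·0.60 + (12 − 3w)·0.90)] / (12n)
- Collected samples only: [(n − k)·12·0.40 + k·3w·0.60] / [(n − k)·12 + k·3w]

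Take k = 5 on saline, k = 2 on lidocaine and w = 2:

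- Full: saline (81.6 + 45.0)/264 = 48.0%; lidocaine (96.0 + 18.0)/264 = 43.2%; difference 4.8 points.
- Collected only: saline (81.6 + 18.0)/234 = 42.6%; lidocaine (96.0 + 7.2)/252 = 41.0%; difference 1.6 points.

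For exits at the end of week 1 or 3, the full difference is 5.8 or 3.8 points and the collected-only difference 0.9 or 2.2. With equal exits (2 and 2) both differences are 0.

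**Simulation of the rule.** Monte Carlo with 400,000 participants per arm. Assumptions: relapse in 60% of controls and 35% on lidocaine, at a uniform time over the four weeks; 90% of screens positive after relapse and 5% before; three consecutive positives stand in for worsening; a stated share of those participants is terminated at that point. The full-data difference in percent positive is about 11.6 points.

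| Share terminated | 10% | 25% | 50% | 100% |
|---|---|---|---|---|
| UDS never collected, control v lidocaine (%) | 1.7 v 1.0 | 4.2 v 2.5 | 8.3 v 4.9 | 16.8 v 9.7 |
| People cut short, of 22 per arm | 0.9 v 0.5 | 2.3 v 1.4 | 4.6 v 2.7 | 9.2 v 5.3 |
| Difference, pooled collected samples | 11.3 | 10.8 | 9.9 | 7.5 |
| Difference, per-person means | 11.4 | 11.1 | 10.6 | 9.7 |
| Difference, missing scored positive | 11.6 | 11.7 | 11.9 | 12.4 |
| Difference, completers only | 11.3 | 10.7 | 9.3 | 2.9 |

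A separately coded rerun agreed within about 0.2 points.

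**If the referred treatment works.** Suppose it halves later positivity to 45%. The true four-week difference is then 11.2, 10.8, 9.9 and 8.3 points across the four columns, while scoring missing screens as positive gives 11.6, 11.7, 11.8 and 12.1. That convention then overstates the effect.

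**No effect.** With 50% relapse in both arms, none of the analyses shows a spurious difference.

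**Power** (t-test, 22 per arm, two-sided 0.05). At 70% v 30% relapse: 0.56 with full data, 0.53 to 0.56 with per-person means, 0.56 with missing scored positive, and 0.54, 0.51, 0.44 and 0.26 for completers. At 60% v 35%, power is about 0.26 for all of these except completers.

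**Primary Aim 1.** Even if everyone who triggers is terminated, only 3.9% v 2.3% (0.9 v 0.5 of 22) stop at the third screen, about the time of Study Day 3.

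**The case against.** The strongest reply is that the text does not literally say that UDS and craving visits stop, and that the document is an IRB template form which cites a section (IV.E.4) it does not contain. Rules on retention and missing data may sit in a fuller plan. This stands as a limit on certainty. Still, leaving the study ordinarily includes leaving its assessments, and nothing supplied says otherwise.

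Second, the stand-in trigger is broader than the rule, which also requires a need for more care. Three consecutive positives is one week of visits and flags 9.2 of 22 controls. The rows for 50% and 100% termination have no support in the document, and no document proposes a completers-only analysis. This also stands: the large losses are the far end of a range, not a forecast. At 10% termination the bias is negligible, and with per-person means power hardly moves at any rate.

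Third, stopping at referral is a defensible choice in a proof-of-concept trial, since later samples partly reflect other treatment. But that would be a different target from the four-week comparison in Section 5, and would have to be stated.

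These points bear on weight. They do not remove the conflict between a four-week outcome and an outcome-related exit.

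**Conclusion.** The concern holds and should be fixed; confidence is medium. As written, Section 15 ends participation for a reason tied to the Primary Aim 2 outcome, and no supplied text keeps those participants under assessment. The omitted statistical section is permitted and is not counted as an error.

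The effect on P2a runs from negligible, if few are terminated, to a difference cut from 11.6 to 2.9 points, if all who trigger are terminated and only completers are analysed. Under the other analyses the range is 7.5 to 12.4 points. The bias is towards no difference, except when missing screens are scored positive. These figures rest wholly on the assumed relapse, positivity and termination rates and cover one pairwise contrast, whereas P2a has two comparators. The effect on P2b was not quantified; the effect on Aim 1 is small.

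**What to change.** Leave the referral rule as it is and change only the clause that ends participation:

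- Consenting participants who are referred continue the scheduled UDS and craving assessments to week 4.
- All randomised and infused participants are analysed in their assigned arm regardless of referral, and the stated target is use and craving over four weeks whether or not the participant was referred.
- The date of referral is recorded.
- Handling of UDS refused after referral is prespecified, for example scored positive with an observed-data sensitivity analysis, because neither is safe in every scenario. Handling of missing craving scores is specified separately.
- Referrals and terminations are reported to the monitoring board by arm.

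The cost is a wording amendment, with any matching consent text, and one recorded date; the 12 UDS visits are already scheduled. The drawbacks are extra retention effort, including for people who may be in another programme, and later samples that partly reflect that treatment.
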